#### **6.7.3.3 Prohibited Concomitant Therapy**

The sponsor must be notified in advance (or as soon as possible thereafter) of any instances in which prohibited therapies are administered.

The following medications are prohibited during the trial (from the first dose of GEN3014 or daratumumab SC):

- Any systemic anti-cancer therapy, eg, chemotherapy, immunotherapy, radiotherapy or experimental therapy, other than GEN3014 or daratumumab SC, including medication that targets CD38, is prohibited.
- Medications used for other indications that have anti-myeloma properties (for example, interferon and clarithromycin ([Ghosh et al., 2013](#); [Niesvizky et al., 2008](#); [Rossi et al., 2013](#)))
- Corticosteroid that exceeds a total daily dose of 10 mg of prednisolone or equivalent administered for more than 10 days unless for the management of AEs (excluding corticosteroids given as GEN3014 pre-infusion and post-infusion medication as prophylaxis for IRRs, as described in Section [6.2.1](#)).
- IV contrast is not used in CT scanning of subjects with secretory MM because of the risk to the kidney. If administration of IV contrast is necessary, then adequate precautions including hydration are indicated.
- Emergency orthopedic surgery or radiotherapy. Continuation of trial drug during or after emergency orthopedic surgery or radiotherapy because of subject benefit may only occur in the absence of disease progression and after consultation with and approval by the sponsor. Such emergency radiotherapy may consist of localized radiotherapy for pain control or for stabilization of an extensive bone lesion at high risk of pathologic fracture or damage to surrounding tissues in a subject in whom delay of systemic therapy is not appropriate. Such radiotherapy is to occur within the first 6 to 8 weeks of treatment and the absence of evidence of disease progression is to be reviewed and approved by the sponsor. If emergency radiotherapy during trial drug administration is required, eg, for bone pain or risk of fracture, this is allowed when there is no evidence of disease progression and approved by sponsor.
- Refer to Section [10.15](#) for local health authority requirements.

#### **6.7.4 Rescue Medicine**

Rescue medication to reverse the action of GEN3014 or daratumumab SC is not available.

### **6.8 Treatment after the End of the Trial**

#### **6.8.1 Subject Contact and Trial Treatment After the End of the Trial**

Investigators may contact the subject to obtain long-term follow-up information regarding the subject's safety or survival status as noted in the ICF (refer to Informed Consent in Section [10.1.5](#), Informed Consent Process).

#### **6.8.2 Continued Access to Trial Drug After the End of the Trial**

For subjects with a potential treatment benefit, subjects may be eligible for continued treatment with Genmab IMP(s) by an extension protocol or as provided for by the local country's regulatory mechanism. However, Genmab reserves the unilateral right, at its sole discretion, to determine whether to supply Genmab IMP(s) and by what mechanism, after termination of the trial and before the product(s) is/are available commercially.

## **7 DISCONTINUATION OF TRIAL TREATMENT AND SUBJECT DISCONTINUATION/WITHDRAWAL**

### **7.1 Discontinuation of Trial Treatment**

A subject's trial drug must be discontinued if:

- Adverse event requiring treatment discontinuation according to stopping rules in Section 6.6.2 (for GEN3014) and Section 6.6.3 (for daratumumab SC)\*
- Subject non-compliance
- The subject initiates treatment with a prohibited medication
- The subject received concurrent (non-protocol) treatment for MM, AML, or DLBCL.
- Sponsor decision
- Subject request to discontinue trial treatment\*
- Pregnancy
- Clinical progression\*
- Disease progression (according to response criteria, Section 8.2)
- Other

\*Every effort should be made to continue evaluations according to the trial protocol. When a subject discontinues trial drug, the subject remains in the trial and is followed until meeting 1 of the reasons listed in Section 7.2.

If a subject's trial drug must be discontinued before the end of the treatment regimen, this will not result in automatic withdrawal of the subject from the trial. The End of Treatment assessments should be performed. In addition, the subject will still be followed for the safety follow-up visit (see Section 7.1.1) and for survival status (see Section 7.1.2) through the end of the trial.

Subjects should be examined regularly according to the Schedule of Activities (Section 1.3), or more frequently, as needed. If the decision to discontinue trial drug occurs around the time of the next planned treatment administration visit, the assessment schedule for the End of Treatment Visit should be followed. Subjects should be followed for safety as detailed in Section 7.1.1 and Section 10.3.

After treatment discontinuation, the subject should receive suitable treatment as decided by the investigator (see Section 6.8).

Trial treatment assigned to the withdrawn subject may not be assigned to another subject. Additional subjects will be entered to ensure the protocol-specified number of subjects complete the trial.

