Bone marrow aspirate  and bone marrow biopsy	8.2.2.2		X	During treatment, collect at Cycle 2 Day 1 (+3 days), Cycle 3 Day 1 (±7 days), then every 3 cycles (±1 cycle). 								X			
Peripheral blood assessment 	8.2.2.1		X	X 					X 		X 	X			
CT/MRI for extramedullary disease 	8.2.2.3	Subject with history of plasmacytomas or if clinically indicated at Screening.	X 	Measure every 8 weeks, and when clinically indicated 								X			

Cycle(s)	Pro- tocol Section	Notes	Screen- ing	Q1W (Weekly)					Q2W		Q4W	UNS	End of Treatment	Safety Follow- up 	Survival Status/ contact 
				Cycle 1-2					Cycles 3-6		Cycle 7 onward				
Cycle Day			D -21 to D -1	D1 	D2 (C1 only)	D8	D15	D22	D1	D15	D1		ASAP after last dose	30d after last dose	Q3M
Visit Window							±3d		±3d		±3d		+7d	+7d	±7d
Response assessment	8.2.2	Response assessment to be performed on Day 1 of each cycle, starting with C2D1		X (C2)					X		X	X	X		
END OF TREATMENT															
New anti-cancer therapy	7.1.1													X	X
Survival Status	7.1.2														X

ADA=anti-drug antibody; AE=adverse event; ASAP=as soon as possible; C=cycle; CBC=complete blood count; CMV=cytomegalovirus; CR=complete remission; CT=computed tomography; D/d=day; ECG=electrocardiogram; ECOG PS=Eastern Cooperative Oncology Group performance status; h=hour(s); HBV=hepatitis B virus; HCV=hepatitis C virus; ICF=informed consent form; Ig=immunoglobulin; IRR=infusion-related reaction; min=minute(s); MRD=minimal residual disease; MRI=magnetic resonance imaging; PK=pharmacokinetic(s); Q3M=every 3 months; Q1W=every week; Q2W=every 2 weeks; Q4W=every 4 weeks; R/R AML=relapsed or refractory acute myeloid leukemia; SAE=serious adverse event; TLS=tumor lysis syndrome; UNS=unscheduled.

- Subjects discontinuing from treatment for any reason will have a safety follow-up visit 30 days (+7 days) after the last dose of GEN3014. If the subject initiates new anti-cancer therapy within 60 days of the last dose of GEN3014, the safety follow-up visit should be performed prior to starting new anti-cancer therapy. Once new anti-cancer treatment is initiated, the subject will move into survival status follow-up.

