DLBCL DISEASE: ASSESSMENTS INCLUDING CENTRAL AND LOCAL LABORATORY ASSESSMENTS															
Immunoglobulins (IgA, IgG, IgM)	8.3.6.2	Also see Table 10-1	X												
Tumor biopsy	8.8.1	A portion of biopsy will be used for biomarker evaluations. Also see Table 1-11	X						X  (C3)				X 		
DLBCL with bone marrow involvement: bone marrow aspirate/biopsy	8.2.3.2	Biopsy obtained as routine standard of care may be used, if taken up to 42 days before C1D1. A portion of bone marrow aspirate/ biopsy will be used for biomarker evaluations. Also see Table 1-11 .	X	Bone marrow biopsy plus aspirate is required for confirmation of an observed radiologic CR; should be done within 30 days of the initial documentation of radiologic CR								X			
FDG-PET-CT/ CT/MRI	8.2.3.1		X	Required at: C2 (W6), C3 (W12), C5 (W18), C6 (W24), then every 24 weeks thereafter (Cycle 12, 18, 24, etc.) until confirmation of disease progression, start of new anti-cancer therapy, withdrawal of consent, or death, whichever comes first								X			

Cycle(s)	Pro- tocol Section	Notes	Screen- ing	Q1W (Weekly)					Q2W		Q4W	UNS	End of Treat- ment	Safety Follow- up 	Survival Status/ contact 
				Cycle 1-2					Cycles 3-6		Cycle 7 onward				
Cycle Day			D -21 to D -1	D1 	D2 (C1 only)	D8	D15	D22	D1	D15	D1		ASAP after last dose	30d after last dose	Q3M
Visit Window							±3d		±3d		±3d		+7d	+7d	±7d
MRI or CT of the brain	8.2.3.1	Perform at Screening only if brain involvement is suspected	X	May be performed during the trial if clinically indicated.											
Response assessment	8.2.3	Response required per efficacy assessment time points		Required at: C2 (W6), C3 (W12), C5 (W18), C6 (W24), then every 24 weeks thereafter (Cycle 12, 18, 24, etc.) until confirmation of disease progression, start of new anti-cancer therapy, withdrawal of consent, or death, whichever comes first								X			
END OF TREATMENT															
New anti-cancer therapy	7.1.1													X	X
Survival Status	7.1.2														X

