Bone marrow aspirate  and/or bone marrow biopsy	8.2.1.3	Assess disease at baseline, confirm CR/sCR, assess MRD, and for other biomarker evaluations (see Table 1-13 and Table 1-14 )	X 	Collect at time of suspected CR/sCR. Also collect at 6, 12, 18, 24 and 30 (±1) months post C1D1 for subjects who achieve CR/sCR and remain on trial. At investigator's discretion, may be repeated if clinically indicated. 								X	X 		
Assess extramedullary plasmacytomas 	8.2.1.4	Subject with history of plasmacytomas, or if clinically indicated at Screening.	X 	Measure every 4 weeks for physical examination (if applicable) and every 12 weeks for imaging assessment 								X			
Response Assessment	8.2.1	To be performed starting C2D1		X (C2)					X		X	X	X		
END OF TREATMENT															
New anti-cancer	7.1.1													X	X

Cycle(s)	Pro- tocol Section	Notes	Screen- ing	Q1W (Weekly)					Q2W		Q4W	UNS	End of Treat- ment	Safety Follow- up 	Survival Status/ contact 
				Cycles 1-2					Cycles 3-6		Cycle 7 onward				
Cycle Day			D -21 to D -1	D1 	D2 (C1 only, GEN- 3014)	D8	D15	D22	D1	D15	D1		ASAP after last dose	30d after last dose	Q3M
Visit Window							±3d		±3d		±3d		+7d	+7d	±7d
therapy															
Survival Status	7.1.2														X

ADA=anti-drug antibody; AE=adverse event; ASAP=as soon as possible; C=cycle; CMV=cytomegalovirus; CR=complete remission; CT=computed tomography; CCI=central laboratory; D/d=day; ECG=electrocardiogram; ECOG PS=Eastern Cooperative Oncology Group performance status; FFPE=formalin-fixed, paraffin-embedded; FLC=free light chain; h=hour(s); HBV=hepatitis B virus; HCV=hepatitis C virus; HIV=human immunodeficiency virus; ICF=informed consent form; Ig=immunoglobulin; IRR=infusion-related reaction; min=minute(s); MM=multiple myeloma; MRD=minimal residual disease; MRI=magnetic resonance imaging; PD=progressive disease; PK=pharmacokinetic(s); Q3M=every 3 months; Q1W=every week; Q2W=every 2 weeks; Q4W=every 4 weeks; RRMM=relapsed or refractory multiple myeloma; SAE=serious adverse event; sCR=stringent complete response; SPEP=serum protein electrophoresis; TLS=tumor lysis syndrome; UNS=unscheduled; UPEP=urine protein electrophoresis.

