### **8.2.1 Efficacy Assessments for RRMM**

Assessment of tumor response and disease progression will be conducted in accordance with the IMWG Response Criteria (Kumar et al., 2016). Disease evaluations will include measurements of myeloma proteins, bone marrow examinations, skeletal surveys, assessment of extramedullary plasmacytomas, and measurements of  $\beta$ 2-microglobulin, albumin, and serum calcium corrected for albumin. Disease evaluations must be performed every 28 days ( $\pm 3$  days) as defined in Table 1-1 (Dose Escalation), Table 1-5 (Expansion Part A [GEN3014 Single Cohorts]), and Table 1-12 (Expansion Part B [Randomized H2H]) until disease progression according to IMWG Response Criteria (see Section 10.9). All response categories require 2 consecutive assessments made at any time, prior to initiating a new therapy. As minimal residual disease (MRD) will also be evaluated, these criteria will be included per IMWG Response Criteria (Section 10.9); see Section 8.8.3 for more information on assay and methodology.

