### **8.2.2        *Efficacy Assessments for R/R AML***

For AML, the revised IWG 2003 criteria (Cheson et al., 2003) will be used for efficacy assessment. Evaluation of response during trial treatment will be based on blood and bone marrow assessment as well as presence or absence of extramedullary disease. Disease evaluations must be performed in every cycle as defined in Table 1-2 (Dose Escalation) and Table 1-6 (Expansion Part A [GEN3014 Single Cohorts]), until disease progression according to AML treatment response criteria. Refer to Section 10.11 for detailed response criteria. Response assessment will be conducted locally by the trial investigator(s).

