**Table 5: Analysis visit windows for efficacy summary listings in R/R DLBCL**

Analysis period	Target day (visit window per protocol)	Analysis visit window	Label on output
Baseline	1 (pre-dose C1D1)	Last data point prior to dosing	Baseline
Scheduled on-treatment disease assessments Week 6,	42 ( $\pm 3$ )	1 to 63	Week 6
	84 ( $\pm 3$ )	64 to 105	Week 12

12, 18, and 24, then every 24 weeks thereafter	126 ( $\pm$ 3)	106 to 147	Week 18
	168 ( $\pm$ 3)	148 to 252	Week 24
	336 ( $\pm$ 3)	253 to 420	Week 48
	...	...	...
Unscheduled	-	-	Unscheduled <Day x>
End of treatment	-	-	End of treatment

Response assessments should be performed until confirmation of disease progression, start of new anti-cancer therapy, withdrawal of consent, or death, whichever comes first.

Details on how to slot subject data that systematically is performed off schedule is provided in the ADaM specification, but no data should be disregarded for efficacy evaluations due to this windowing.

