**Table 8: Censoring scheme for time to event variables**

Situation	Date of Progression or Censoring	Censoring Rule
Incomplete or no baseline assessments	C1D1, or date of randomization	Censored
No documented PD or death prior to analysis data cutoff, trial discontinuation, start of new anti-cancer treatment	Date of last valid tumor assessment with no documented PD before the situation*	Censored
Documented PD between adequate** assessment visits	First date of assessment demonstrating documented PD	Event
Death before first response assessment	Date of death	Event
Death between adequate** assessment visits	Date of death	Event
Death or documented PD after two or more consecutive missed visits***	Date of last valid tumor assessment prior to the missed visits*	Censored

\*Excluding response assessments with NE as overall time point response. If no such assessment exists, the censoring date will be C1D1.

\*\* No more than one missed visit, no anti-cancer therapy etc. before the death or documented progression.

\*\*\* Please refer to the DPS for the definition of two missed scans.

Clinical progression (as recorded in eCRF) does not constitute documented progression and will cause censoring (unless documented progression was recorded before clinical progression).

DOR will be estimated using the KM method and the result will be displayed graphically. The number and percentage of subjects with event or censoring will be reported. Median DOR (months) with associated 95% CI as well as first and third quartiles and range will be provided.

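### Five myeloma and AML schedules end response assessment at End of Treatment, although Protocol Section 8.2 requires it until progression; following the schedules can censor PFS and DOR informatively

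*Protocol*

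**What the plan says.** **Duration of assessment, Protocol text.** Section 8.2.1 requires myeloma evaluations every 28 days (±3) "until disease progression according to IMWG Response Criteria (see Section 10.9"). Section 8.2.1.1 gives the serum and urine samples the same end point. Section 8.2.2 requires AML evaluations each cycle "until disease progression according to AML treatment response criteria". Sections 8.2.1 and 8.2.2 refer to the schedule tables for the visits.

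**Duration of assessment, schedules.** In the myeloma tables (1-1, 1-5, 1-12) the response row is annotated "To be performed starting C2D1". In the AML tables (1-2, 1-6) it reads "Response assessment to be performed on Day 1 of each cycle, starting with C2D1". In all five the last planned mark is at End of Treatment, and the Safety Follow-up and Survival Status columns are blank. The SPEP/UPEP rows of the myeloma tables end at the same point. Only the DLBCL table (1-7) carries response assessment on "until confirmation of disease progression, start of new anti-cancer therapy, withdrawal of consent, or death, whichever comes first".

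**After stopping drug.** Section 7.1 says "the subject will still be followed for the safety follow-up visit (see Section 7.1.1) and for survival status (see Section 7.1.2) through the end". Its asterisk note, attached to adverse event, subject request and clinical progression, asks sites to try to keep up protocol evaluations.

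**Analysis.** SAP Section 5.1.2, directly below the DLBCL window table, says "Response assessments should be performed until confirmation of disease progression, start of new anti-cancer therapy, withdrawal of consent, or death, whichever comes first". SAP Table 8 censors at the last valid assessment when no progression or death is documented. It also censors "Death or documented PD after two or more consecutive missed visits" back to the assessment before the gap, and leaves the definition of a missed scan to the Data Presentation Specification (DPS). Text below the table censors clinical progression unless progression was documented earlier.

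**The concern.** A site working from the schedule has no planned disease assessment for a subject who stops drug before documented progression. The remaining contacts are a 30-day safety visit and 3-monthly survival contact, which may be a telephone call or email. IMWG progression rests largely on laboratory values, so such contact will rarely document it.

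The SAP then censors that subject at the last assessment. Subjects who stop for toxicity or deterioration may be at higher risk of progression or death than those who stay on drug. If so, the censoring is informative and the PFS and DOR curves are too high. The gap falls where the plan wants estimates: Protocol Section 4.4.1.3 expects about 4 months of treatment and 17 months of follow-up in Part B, and SAP Section 5.4.5 reports PFS at 6, 9 and 12 months.

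**Working it through.** **Step 1: the passages side by side.**

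| Place | Response assessment runs until |
|---|---|
| 8.2.1, 8.2.1.1 (myeloma) | progression |
| 8.2.2 (AML) | progression |
| Footnotes, Tables 1-1, 1-5, 1-12 | confirmed progression, but the 28-day SPEP/UPEP is called on-treatment |
| Rows of Tables 1-1, 1-2, 1-5, 1-6, 1-12 | End of Treatment |
| 7.1, main text | not named; only safety visit and survival status |
| 7.1, asterisk note | continues per protocol, if possible |
| Table 1-7 (DLBCL) | progression, new therapy, withdrawal or death |

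Sampling continues past End of Treatment in one case. Marrow/MRD is timed at 6, 12, 18, 24 and 30 months from C1D1 for myeloma complete responders who remain on trial (Tables 1-4, 1-9, 1-15), and for Part A AML subjects in CR or CRi (Table 1-10).

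**Step 2: consequence under SAP Table 8.** Suppose no assessment takes place after End of Treatment. Progression or death soon afterwards, if documented, is still an event. With 28-day visits, an event more than about two cycles (2 × 28 = 56 days) later is censored back to the last assessment, if never-scheduled visits count as missed. The DPS settles that, and it is not among the documents.

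**Step 3: size, for scale only.** The documents give no PFS event target and no discontinuation rate, so there is no planned figure to reproduce. Assumptions, none from the documents:
- the on-drug hazard λ = ln 2 / M, with median M = 4 months
- a share f stops drug before progression, at constant rate μ = λf/(1−f)
- the hazard after stopping is kλ.

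Censoring every stopper at End of Treatment makes Kaplan-Meier estimate exp(−λt), so its median is M. Full follow-up gives

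S(t) = exp(−at) + c·[exp(−kλt) − exp(−at)], with a = λ/(1−f) and c = f/[1 − k(1−f)].

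Example, f = 0.2 and k = 2: λ = 0.1733, a = 0.2166, c = 0.2/(1 − 1.6) = −0.333. At t = 3.76, S = 0.443 − 0.333 × (0.272 − 0.443) = 0.500, so the median is 3.76.

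| Share stopping | k = 1 | k = 2 | k = 4 |
|---|---|---|---|
| 10% | 4.00 | 3.88 | 3.77 |
| 20% | 4.00 | 3.76 | 3.53 |
| 30% | 4.00 | 3.62 | 3.29 |

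The censored analysis reports 4.00 in every cell. The largest overstatement is 4.00/3.29 − 1 ≈ 22%. At k = 1, c = 1 and the bias is zero. The ratio does not depend on M: with M = 6 the extreme cell is 6.00 against 4.93, again 22%. Six-month PFS in the extreme cell is 35% reported against 26%. In a 40-subject arm, 10/20/30% stopping puts 4, 8 or 12 potential events out of reach.

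These figures lean high. They censor every stopper at once, whereas Table 8 keeps documented events that occur before two missed visits. They also attribute to the schedule some losses that new anti-cancer therapy would cause anyway.

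**The case against.** The strongest reply is that the protocol does tell sites to continue. The asterisk note covers the three stopping reasons that matter most here, and Section 8.2.1 gives it content: a 28-day interval and progression as the end point. The myeloma footnotes drop assessments only once progression is confirmed, and unscheduled assessments are allowed. This stands in part. It makes the fault a contradiction rather than a rule that assessment stops. It does not remove the fault, because the note points back to a protocol whose schedule plans no such visits, and the main text of Section 7.1 names none.

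A reader might infer four stronger things that the documents do not support:
- **That these subjects are in fact informatively censored.** This depends on which text sites follow and on whether risk changes at stopping. The documents give data on neither.
- **That nothing is collected after End of Treatment.** The marrow/MRD sampling of complete responders contradicts this.
- **That the SAP explicitly requires assessment to progression in myeloma and AML.** The sentence in SAP Section 5.1.2 stands under the DLBCL table and repeats that cohort's wording. Its wider reach is probable, not stated.
- **That the Part B comparison is biased.** The reaction-related stopping rules differ between arms (Protocol Sections 6.2.3 and 6.2.4.3), but no rates are given and no PFS test or hazard ratio is planned.

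It is also fair to say that no hypotheses are pre-defined, so the consequence is limited to secondary, descriptive estimates.

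**Conclusion.** The conflict between Section 8.2 and the five schedules is real and should be reconciled. If the schedules are followed as printed, PFS and DOR lose events that the protocol elsewhere says to collect, and the resulting censoring can be informative. The size cannot be determined from the documents. The 0 to 22% range for the median rests wholly on the assumed stopping shares, constant hazards and a post-stop hazard of 1 to 4 times. Whether later deaths are also lost depends on the DPS definition.

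The SAP's censoring of clinical progression is a separate rule. It would remain after the schedules are corrected, and it concerns the stopping reason most plausibly linked to imminent progression. ORR, the primary expansion endpoint, is little affected. This is a worthwhile correction to secondary endpoints, not a threat to the trial's main objectives.

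**What to change.** 1. **Protocol Section 7.1 and Tables 1-1, 1-2, 1-5, 1-6, 1-12.** For subjects without documented progression, carry the response rows and the M-protein (myeloma) or blood (AML) rows past End of Treatment. Use the Section 8.2 interval and the Table 1-7 end points: progression, new anti-cancer therapy, withdrawal of consent or death. Make the main text of Section 7.1 agree with its asterisk note.
2. **SAP Table 8.** State that visits the schedule never planned are not missed visits, so that a death after stopping drug and before new therapy is an event. Align the DPS.
3. **SAP, PFS and DOR.** Add a sensitivity analysis that counts clinical progression, and progression or death after missed visits, as events. Changes 1 and 2 do not alter the clinical-progression rule.

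Change 1 needs a protocol amendment and samples from subjects who stop without progression; Section 8.2 already requires those assessments. Changes 2 and 3 cost wording and one extra analysis, with no new visits. Change 1 should be made while subjects are still being followed, because unassessed progression dates cannot be reliably recovered later.
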